As this is a first in-human study, a single subject will receive the first dose of ¹²⁴I-PEG-AVP0458. Further dose administration will be sequential within each cohort to mitigate risks of anaphylactic or any other acute unexpected reactions. Administration of doses within a cohort will be staggered by 24 hours, i.e. there will be a period of 24 hours between the first, second and subsequent subjects in a cohort to observe and interpret reactions and adverse events. This time frame is sufficient to exclude any possible acute allergic or anaphylactic reactions to PEG-AVP0458.

After completion of accrual into the first cohort (1 mg/m 2 dose), the Trial Management Committee will review the safety data from these participants before a decision is made to escalate the dose to 10 mg/m 2 .

If no patients entered in the 1^{st} dose group experience a dose-limiting toxicity (DLT), and the Trial Management Committee agree, then the 2^{nd} dose group may commence on the higher dose of 10 mg/m^2 30 days after the last patient on the first dose group has received the 124 I-PEG-AVP0458 infusion. If any one patient in either cohort of 3 patients experiences a DLT, then 3 additional patients will be entered in that dose group. If additional patients are treated in the 1^{st} dose group, all patients entered must have been observed for 30 days before a new patient may receive an infusion in the 2^{nd} dose group. If greater than or equal to two DLTs are observed at a dose, then the MTD is considered to have been exceeded.

If at most, one DLT is observed, the next 3 patients are assigned to the next highest dose. If two or more DLTs are observed, then the MTD is considered to have been exceeded.

A DLT is defined as any of the following events occurring within 30 days of study drug administration:

- Any Grade 2 or greater allergic reaction.
- Any Grade 3 toxicity. Exceptions are: fever; asymptomatic hyperglycemia; hypophosphatemia; nausea, vomiting, or diarrhoea despite the use of optimal supportive medical therapy; leukopenia or thrombocytopenia that revert to baseline within three weeks of occurrence; lymphopenia without other dose-limiting events (eg opportunistic infection).
- Any Grade 4 toxicity.

The 30 days will allow identification and mitigation of the risks of any delayed immunogenic reaction before progressing to a subsequent cohort.

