In the event 2 or more patients experience DLT at the first dose level, an additional 3 patients will be entered at a 0.5mg/m² dose level.

After the last evaluation of the last patient enrolled in the second dose group (10 mg/m²), an interim analysis of the safety and dosimetry data will be undertaken. This analysis will be considered by the Trial Management Committee to ascertain which of the two doses, 1 or 10 mg/m², produces the better safety profile and dosimetry results for PEG-AVP0458. The dose selected will be based on imaging characteristics and pharmacokinetic data of ¹²⁴I-PEG-AVP0458 at each dose level. This chosen dose will be used to infuse the last 6 patients in the second part of the clinical study. This last group will enrol 3 patients with prostate cancer and 3 with ovarian cancer and will continue to evaluate safety as the primary endpoint.

Because of the low PEG-AVP0458 doses tested in this study, the fact that only two dose levels are being evaluated, and the past clinical experience with the intact parent antibody (CC49), this study is not expected to identify a maximum tolerated dose. It should be noted that the tracer dose of ¹²⁴I-labelled to PEG-AVP0458 has not been reported to be associated with adverse events in prior clinical trials of ¹²⁴I-labelled compounds.

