5.9.2 Modifications for events occurring during or immediately after ¹²⁴I- PEG-AVP0458 infusion

There is a potential for the occurrence of allergic-type reactions during and immediately following the administration of ¹²⁴I-labelled PEG-AVP0458. If this occurs, the rate of infusion should be decreased or the infusion terminated completely in accordance with the following guidelines:

	Action ¹			
	Decrease rate of	Stop		
Clinical Manifestation	¹²⁴ I-PEG-AVP0458 Infusion by 50%	¹²⁴ I-PEG-AVP0458		
		Infusion ²		
↓ Systolic BP of 25-50 mmHg	X			
↓ Systolic BP of >50 mmHg		X		
Bronchospasm		X		
Severe shortness of breath		X		
Rigors	X			
Chills	X			

- 1 = Investigator discretion is necessary for a decision to reduce the rate or stop ¹²⁴I-PEG-AVP0458 infusion.
- 2 = The infusion may be re-initiated within 1 hour at the discretion of the Investigator. Should the clinical situation require that therapy be stopped again, the ¹²⁴I-PEG-AVP0458 infusion will not be restarted and the patient will be removed from study.

Management of Toxicities 5.9.3

Precautions for anaphylaxis must be available. Equipment for assisted ventilation and an established free flowing line must be available at the time of each infusion.

A life-threatening anaphylactic response of a sensitized human may appear within minutes after administration of a specific antigen and is manifested by respiratory distress often followed by vascular collapse or by shock without antecedent respiratory difficulty. Cutaneous manifestations are exemplified by pruritus and urticaria with or without angioedema and may be characteristic for systemic anaphylactic reactions. Gastrointestinal manifestations may include nausea, vomiting, crampy abdominal pain, and diarrhoea.

Diagnosis of anaphylaxis or choice of treatment and drug dosing is in the responsibility and at the discretion of the individual Investigator.

Appropriate supportive therapeutic interventions may be initiated at any time. Treatment with IV corticosteroids, antihistamines, pethidine, paracetamol, or adrenaline should be considered in the event of an allergic reaction or hypersensitivity. Refer to Appendix 2 for definition of allergic reaction or hypersensitivity according to CTCAE v4.0.

These events will be recorded in the patient's medical history and eCRF.

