5.10 Criteria for Dose Escalation and Dose Selection

The Trial Management Committee is responsible for decisions regarding dose escalation (moving dose group 1 to group 2) and dose selection (moving from group 2 to 3), based on safety and dosimetry data.

For dose escalation, the decision is based on safety. If no patients in dose group 1 experience a DLT, then dose group 2 may commence 30 days after the last patient on the dose group 1 has received the PEG-AVP0458 infusion.

If any one patient in either cohort of 3 patients experiences a DLT, then 3 additional patients will be entered in that dose group. If additional patients are treated in the dose group 1, all patients entered must have been observed for 30 days before a new patient may receive an infusion in dose group 2. If greater than or equal to two DLTs are observed at a dose, then the MTD is considered to have been exceeded. If at most, one DLT is observed, the next 3 patients are assigned to the next highest dose. If two or more DLTs are observed, then the MTD is considered to have been exceeded.

In the event 2 or more patients experience DLT at the first dose level, an additional 3 patients will be entered at a 0.5mg/m² dose level

The Trial Management Committee will evaluate safety and dosimetry data available after the dose escalation part of the study (Interim Analysis) and determine the dose to be administered to the last 6 patients in the study.

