6.1 Safety Evaluation

Safety of ¹²⁴I-PEG-AVP0458 will be determined by the ongoing monitoring of the incidence and intensity of AEs graded using the National Cancer Institute Common Terminology Criteria for Adverse Events (CTCAE) v4.0 (Appendix 2), with special emphasis on DLT events and infusional toxicities. A copy of CTCAE v4.0 also may be downloaded from the Cancer Therapy Evaluation Program home page (http:\\ctep.info.nih.gov).

A DLT is defined as any of the following events occurring within 30 days of study drug administration:

- Any Grade 2 or greater allergic reaction.
- Any Grade 3 toxicity. Exceptions are: fever; asymptomatic hyperglycemia; hypophosphatemia; nausea, vomiting, or diarrhoea despite the use of optimal supportive medical therapy; leukopenia or thrombocytopenia that revert to baseline within three weeks of occurrence; lymphopenia without other dose-limiting events (eg opportunistic infection).
- Any Grade 4 toxicity.

To be dose-limiting, a toxicity must be possibly, probably, or definitely related to the administration of ¹²⁴I-PEG-AVP0458. All DLTs must be discussed with the study Coordinating Principal Investigator.

AEs will be collected after the patient has been enrolled. AEs occurring after signing informed consent but prior to receiving study drug (ie before enrolment) should only be reportable if related to study procedures. All AEs occurring after enrolment must be recorded until 30 days following the end of treatment exposure. Refer to Section 7.2.1. AEs include adverse drug reactions, any unfavourable sign or symptom (related and unrelated), illnesses with onset during the study, or exacerbations of pre-existing illnesses or conditions. Progression of the patient's malignancy should not be considered an AE, unless, in the Investigator's opinion, study treatment resulted in an exacerbation of the patient's condition. Exceptions are if disease progression results in death or hospitalization while on study or within 30 days of the last dose. If either occurs, progressive disease will be reported as a SAE (see Section 8.2.2) and will also be documented on an AE eCRF. All observed or volunteered AEs, regardless of treatment group or suspected causal relationship to study drug, will be recorded on the AE eCRF.

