Clinically significant changes in physical examination findings and new abnormal objective test findings (i.e. laboratory, x-ray, ECG) should also be recorded as AEs. The criteria for determining whether an abnormal objective test finding should be reported as an AE are as follows:

- associated with accompanying symptoms,
- requires additional diagnostic testing or medical/surgical intervention,
- leads to discontinuation from the study,
- requires additional concomitant drug treatment or other therapy, or
- considered clinically significant by the Investigator or Sponsor.

Any abnormality on blood testing should be confirmed by a repeat test.

The sign or symptom should be recorded as an AE, not as the objective test finding. (Correct: Hypokalemia. Incorrect: potassium of 3.3 mEq/L)

Minor abnormalities in laboratory tests compared to baseline, and repeat of these tests in the absence of any of the above conditions, do not meet the criteria for reporting as an AE. An abnormal test result that is later determined to be an error does not require reporting as an AE, even if it did meet one or more of the above conditions.

For all AEs, the Investigator must pursue and obtain information adequate to determine the causality (i.e. study drug or other cause) and outcome of the event and to assess whether it meets the criteria for classification as a SAE (see **Section 7.1.2**). Follow-up of the event is required until the event or its sequelae resolve or stabilize at a level acceptable to the Investigator and the study Sponsor/monitor.

There are no anticipated severe AEs associated with the administration of the investigational product, which will be given as a one dose infusion. Clinical experience with the parent antibody, CC49, used in larger doses and in radioimmunotherapy studies, demonstrated hematologic dose-limiting toxicities, but they were most likely due to the radiation dose to red marrow from radioimmunotherapy treatment [19, 40].

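### The DLT definition exempts Grade 3 nausea, vomiting and diarrhoea that persist despite optimal supportive therapy, so refractory GI toxicity does not count in the escalation rules

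*Protocol*

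**What the plan says.** The Protocol defines a DLT twice, in 3.1 and 6.1, with the same three criteria within 30 days of dosing: an allergic reaction of Grade 2 or more, any Grade 3 toxicity outside a list of exceptions, and any Grade 4 toxicity. The GI exception reads "nausea, vomiting, or diarrhoea despite the use of optimal supportive medical therapy" in both places. In the same list, hyperglycaemia is excused only when asymptomatic. The blood-count exceptions are "leukopenia or thrombocytopenia that revert to baseline within three weeks of occurrence" and "lymphopenia without other dose-limiting events (eg opportunistic infection". Fever and hypophosphataemia carry no qualifier.

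Section 6.1 adds a condition that 3.1 lacks: "To be dose-limiting, a toxicity must be possibly, probably, or definitely related to the administration of" the study drug. The schema (Figure 1) refers the reader to 3.1.

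The escalation rules in 3.1 and 5.10 use the DLT count:

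- With no DLT in group 1, "dose group 2 may commence 30 days after the last patient on the dose group 1 has received the PEG-AVP0458 infusion". Section 3.1 also requires the Trial Management Committee to agree.
- With one DLT in a cohort of 3, 3 more patients are entered at that dose.
- With two or more, the MTD has been exceeded. At the first dose level there is also a fallback: "In the event 2 or more patients experience DLT at the first dose level, an additional 3 patients will be entered" at 0.5 mg/m².

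**The concern.** The qualified exceptions around the GI item each excuse the milder form of an event: no symptoms, recovery within a set time, or no complicating event. The GI item does the opposite. It excuses the event that persists through best treatment and, taken literally, still counts a Grade 3 GI event that never received optimal support. The wording looks like a reversal of the usual rule, under which such an event is exempt unless it persists despite optimal therapy.

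The error lowers the DLT count, which is the direction that permits escalation from 1 to 10 mg/m². It also makes counting depend on how an event is labelled. Section 5.9.3, describing systemic anaphylactic reactions, says: "Gastrointestinal manifestations may include nausea, vomiting, crampy abdominal pain, and diarrhoea". The same symptoms count from Grade 2 if recorded as an allergic reaction, but not at Grade 3 if recorded as a GI term.

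**Working it through.** **The plan's own figure.** The Protocol gives no DLT rate or error rate to reproduce. Its sample size does follow from the cohort rules: 3 + 3 + 6 = 12 at minimum, and 6 + 6 + 6 = 18 with both escalation cohorts expanded. This matches the 12–18 in section 3.2 and does not depend on the point at issue.

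**Readings of the exception.** For a related, non-allergic Grade 3 GI event:

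| Reading | Controlled by optimal support | Refractory |
|---|---|---|
| Literal (only refractory events exempt) | DLT | not a DLT |
| Blanket Grade 3 GI exemption | not a DLT | not a DLT |
| Corrected (only controlled events exempt) | not a DLT | DLT |

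On both readings of the present text, the refractory event adds 0 to the count. Grade 4 GI events, and GI symptoms forming part of an allergic reaction of Grade 2 or more, still count.

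**Effect on the rules, with no assumed rate.** Take the first 3 patients at 1 mg/m² and suppose the only relevant events are related, non-allergic, refractory Grade 3 GI events.

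| Patients affected | DLTs as written | Consequence as written | DLTs corrected | Consequence corrected |
|---|---|---|---|---|
| 1 of 3 | 0 | 10 mg/m² may open after 30 days if the committee agrees | 1 | 3 more patients at 1 mg/m² |
| 2 of 3 | 0 | same | 2 | MTD exceeded; 3 patients at 0.5 mg/m² |
| 3 of 3 | 0 | same | 3 | MTD exceeded; 3 patients at 0.5 mg/m² |

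**Illustration with assumed rates.** Let p be the chance that a patient has such an event, with no other DLTs and patients independent. The Protocol gives no value for p; I take 2%, 5% and 10%, and the low end is more plausible here.

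- P(at least one DLT in the first 3) = 1 − (1 − p)³
- P(MTD exceeded at group 1) = 1 − [(1 − p)³ + 3p(1 − p)² × (1 − p)³] = 1 − [(1 − p)³ + 3p(1 − p)⁵]

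| p | (1 − p)³ | 3p(1 − p)⁵ | At least one DLT in 3 | MTD exceeded |
|---|---|---|---|---|
| 0.02 | 0.9412 | 0.0542 | 0.0588 | 0.0046 |
| 0.05 | 0.8574 | 0.1161 | 0.1426 | 0.0266 |
| 0.10 | 0.7290 | 0.1771 | 0.2710 | 0.0939 |

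Under the present wording these events contribute 0 to both probabilities, whatever p is.

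**Cytopenia timing (minor).** The three-week recovery window for Grade 3 leukopenia or thrombocytopenia has closed by Day 30 only if onset was by Day 30 − 21 = Day 9. A later onset can still be unresolved, with its window open, when group 2 may start. The latest qualifying onset, Day 30, closes at Day 51, which is 21 days later. The text does not say how to count a pending case. A cytopenia with onset by Day 9 that has not recovered at Day 30 is already a DLT.

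**The case against.** The strongest reply is that the sponsor may have meant a blanket exemption for Grade 3 GI events, alongside fever and hypophosphataemia, which have no qualifier. That would be a debatable choice and not a slip. But the qualifier would then do no work, and refractory events would still be excluded, so the remedy stands.

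The second reply is that other safeguards exist. The committee reviews safety and must agree before escalation. Section 5.9.1 classes every AE of Grade 2 or more during infusion and the next four hours as an infusional toxicity, and section 6.1 gives these special emphasis. All AEs are summarised by cohort, so the primary safety endpoint is not biased. These points are correct, and they mean that a zero DLT count permits escalation without compelling it. None of them makes the event a DLT or obliges the committee to act on it.

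The third reply is that the consequence is bounded. There is one dose per patient and one escalation step, and the NOAEL is about 100 times the starting dose, so 10 mg/m² is about a tenth of it (10/100). The Protocol does not expect to find an MTD, and section 6.1 states: "There are no anticipated severe AEs associated with the administration of the investigational product". This stands, and it limits practical importance. Two of three patients with refractory Grade 3 vomiting shows how the rule behaves; it is not a forecast.

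The side points are small. The relatedness condition missing from 3.1 would over-count, which is the cautious direction, and 6.1 supplies it. The Grade 4 criterion literally omits a non-allergic Grade 5 event, but deaths are reported immediately. An unrecovered cytopenia arguably already falls outside its exception. They are worth tidying in the same edit, but the main point does not need them.

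**Conclusion.** The concern holds. As written in both 3.1 and 6.1, a related, non-allergic Grade 3 GI event that persists despite optimal supportive therapy is not a DLT, and nothing else in the Protocol restores it. Even 3 of 3 patients with such events would satisfy the no-DLT condition for a ten-fold step in a first-in-human trial. That conclusion rests on the wording alone; the probabilities in the illustration rest on assumed rates. The practical risk is modest, given the toxicity expected and the committee's role, but the counting rule is wrong and should be corrected.

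**What to change.** Use one DLT definition, cross-referenced from the schema and sections 3.1, 5.10 and 6.1, that exempts Grade 3 nausea, vomiting or diarrhoea only if controlled by optimal supportive therapy. In the same edit:

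- carry the relatedness condition from 6.1 into that definition;
- extend the Grade 4 criterion to Grade 4 or 5;
- state that a Grade 3 leukopenia or thrombocytopenia not yet recovered at the decision date counts as a DLT unless escalation is held until its three-week window closes.

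The cost is amendment wording. The planned 12–18 patients are unchanged. Choosing to hold for a pending cytopenia would delay escalation by at most 21 days in that case.

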3.2 Sample Size

An anticipated total of 12-18 patients will be entered into the study. In the dose-escalating part of the study, 6 patients with either prostate or ovarian cancer will be enrolled: 3 in the 1 mg/m² dose group and 3 in the 10 mg/m² dose group. If DLTs occur, the number will increase to a maximum of 12.

In the second part of the study, a further 6 patients will be enrolled, 3 with ovarian cancer and 3 with prostate cancer. They will receive the PEG-AVP0458 dose defined in the interim analysis.

3.3 Study Duration

It is anticipated that patient accrual will require approximately 9 months and the clinical trial will end 12 months after enrolment of the first patient.

3.4 Participating Sites

The participating clinical trial sites for this study are:

- Austin Health
- Peter MacCallum Cancer Centre

Patients with ovarian cancer will also be referred from the Royal Women's Hospital and Mercy Hospital for Women.

Study population

4.1 Patient Recruitment

Patients with recurrent or refractory ovarian cancer or patients with confirmed metastatic prostate cancer, or patients with confirmed primary prostate cancer prior to local therapy (surgery or radiation), will be considered for this trial if their tumours are TAG-72 positive (evaluation performed on archived paraffin blocks) and they have disease deemed likely to be assessable by PET by nuclear medicine physician.

4.2 Inclusion Criteria

Eligibility for the study will be determined by screening tests, physical examination/medical history, and provision of written informed consent and fulfillment of eligibility criteria.

Participants will be considered eligible for enrolment in the study if they comply with all of the following criteria

4.2.1 Ovarian cancer

- Patients with relapsed or refractory ovarian cancer
- TAG-72-positive tumours (see Section 4.4)
- Detectable metastatic disease deemed likely to be assessable by PET by nuclear medicine physician as seen on imaging (see Section 4.5) performed within 21 days of enrolling in the study.
- ECOG Performance Status of 0-1 (Appendix 1)
- Expected survival of \geq 3 months
- 18 years of age or greater
- Platelet count ≥100 x 10⁹/L
- Absolute neutrophil count $\geq 1.5 \times 10^9/L$
- Aspartate Aminotransferase (AST) ≤3x upper limit of normal (ULN), or <5x ULN with liver metastases
- Total bilirubin ≤ 34 μmol/L
- Serum creatinine ≤160 µmol/L
- Provision of written informed consent.

Prostate cancer 4.2.2

- Patients with metastatic prostate cancer, or primary prostate cancer who are preprostatectomy or pre-radiotherapy
- TAG-72-positive tumours (see Section 4.4)
- Detectable disease deemed likely to be assessable by PET by nuclear medicine physician as seen on imaging (see Section 4.5) performed within 21 days of enrolling in the study
- ECOG Performance Status of 0 or 1 (Appendix 1).
- Expected survival of \geq 3 months
- 18 years of age or greater
- Platelet count ≥100 x 10⁹/L
- Absolute neutrophil count $\geq 1.5 \times 10^9/L$
- AST $\leq 3x$ ULN, or < 5x ULN with liver metastases
- Total bilirubin ≤ 34 μmol/L
- Serum creatinine ≤160 µmol/L
- Provision of written informed consent.

4.3 Exclusion Criteria

Participants will not be entered in the study for any of the following reasons:

4.3.1 Ovarian Cancer

- Disease-specific exclusions
 - Evidence of current complete or partial bowel obstruction
 - Need for IV or TPN hydration
- Chemotherapy, immunotherapy, biologic therapy, radiation therapy, or other investigational product within 4 weeks prior to study entry or likely to be required during the 4-week onstudy period
- Patients using corticosteroids or immunosuppressive agents: low dose oral corticosteroids for concomitant medical conditions are permitted. Inhaled or topical corticosteroids are permitted.
- Patients with active infections requiring antibiotics, with bleeding disorders or with other serious illness
- Women who are pregnant (positive hCG test) or lactating
- Women of child-bearing potential who are unwilling to utilize a medically acceptable method of contraception
- Patients with a concurrent active serious medical condition likely to affect participation in the study, such as a documented myocardial infarction ≤3 months prior to screening or unstable angina pectoris.
- Patients unable to sign informed consent or unwilling to comply with the procedural requirements of this clinical protocol.

